## 4.2.d. Study Phase

Phase 3

Is this an NIH-defined Phase III Clinical Trial?

Yes  No

## 4.2.e. Intervention Model

Parallel

## 4.2.f. Masking

Yes  No

Participant  Care Provider  Investigator  Outcomes Assessor

## 4.2.g. Allocation

Randomized

## 4.3. Outcome Measures

Type	Name	Time Frame	Brief Description
Primary	Ignition Interlock Device Lockout Events	9-month follow-up posttest	The primary outcome measure will be frequency of IID lockout events from baseline to 9-month follow-up post-randomization, collected from the Santa Fe DWI Program database for each first-time DWI offender participant.
Secondary	Alcohol Use	Baseline, 3-month follow-up posttest, and 9-month follow-up posttest	Alcohol use by the DWI offender will be assessed with versions of the Form 90 adapted for online assessment for the CFMs (Form 90-ACS) and first-time DWI offenders (Form 90-AF). The Form 90 measures produce detailed quantity and frequency measure of alcohol use for the first-time offender.
Other	Family Functioning Scales	Baseline, 3-month follow-up posttest, and 9-month follow-up posttest	Family functioning will be assessed as a potential mediator of B-SMART effects, with DWI offenders and CFMs with three scales: (1) Family Environment Scale - Cohesion and Conflict subscales assesses offender and CFM perceptions of positive and negative family functioning; the two subscales selected are strongly associated with treatment outcome; (2) Family Communication Scale from FACES-IV assesses perception of quality of communication in the family; (3) Pleasant Events Schedule (adapted) assesses shared positive activities within a family.

Other	System Usability Scale	3-month follow-up posttest and 9-month follow-up posttest	The System Usability Scale consists of ten Likert strongly agree to disagree items that asks the respondent to rate the technology product being reviewed (Example items: I think that I would like to use this product frequently; I found the product very awkward to use; I felt very confident using the product). Participants also provide a final overall rating of the product along a 7-point worst imaginable to best imaginable dimension. This measure will be assessed with DWI offenders and CFMs in the intervention group.
Other	B-Smart Mobile Web App Use	3-month follow-up posttest and 9-month follow-up posttest	A custom program on the KB web server will track use of the B-SMART mobile web app. Users will register and use a password to access B-SMART and this password will be used to track use, keeping data about users private. Click-stream (pages visited), time spent on the B-SMART mobile web app, and number of individual visits to the mobile web app will be recorded.
Other	Demographic Characteristics	Baseline	The CASAA demographics form will collect information on participants' age, education, sex, and ethnicity.

4.4. Statistical Design and Power 4.4\_bsmart.pdf

4.5. Subject Participation Duration 9 months

4.6. Will the study use an FDA-regulated intervention?  Yes  No

4.6.a. If yes, describe the availability of Investigational Product (IP) and Investigational New Drug (IND)/Investigational Device Exemption (IDE) status

4.7. Dissemination Plan 4.7\_bsmart.pdf

## Sample Size Determination

The sample size for the randomized trial in the Phase II research is designed to provide sufficient information for Phase III commercialization. The sample size assumes the counts of interlocks are Poisson distributed. We have assumed 4 interlocks over 9 months in the control arm or a rate of 0.44 per month for each DWI offender. In the *B-SMART mobile web app* group, we have assumed a reduction of 40% from 0.44, resulting in a rate of 0.27 per month. The null hypothesis is that the ratio of these two rates is 1.0 versus 0.6. Assuming a Type I error of 0.05 (2-sided), 90% power, sample size is only 27 DWI offenders per group. However, if the rate is higher up to 1 per month, the sample size required declines since the percent reductions yield wider absolute differences in the rates. We also are keen to know the reductions achievable with the *B-SMART* group, so we evaluated the sample size with regards to other effect sizes. In a Cochrane meta-analysis reported the impact of IIDs to reduce risk by 64%, but with a confidence interval that ranged from 76% to 37%. In the proposed trial, we have two treatment groups and may see less impact than that in the meta-analysis. Thus, a sample size of 119 DWI offenders per group will allow for 90% power with a comparison of 0.44 to 0.36 or approximately a 20% reduction in interlocks. We will adjust for an expected 15% attrition and this sample size also has sufficient sample size to evaluate the impact in various gender and ethnic subgroups. Thus, we propose to randomize 150 DWI offenders and 150 CFMs to each arm of the trial.

## Outcome Analysis Plan

The trial is intended to evaluate the following hypotheses:

**H1:** First-time DWI offenders in the intervention group (*B-SMART mobile web app*) will have significantly fewer IID lockout events than participants in the control group (UC information condition).

**H2:** Lower rates of IID lockout events will be mediated by improvements in Family Functioning, Family Communication, and Shared Positive Family Events in the intervention (*B-SMART mobile web app*) condition compared to the UC information condition.

We will also analyze moderation of the effect of *B-SMART* by demographics and mediation of IID lockout events by *B-SMART* use in the intervention group.

Three levels of analysis are planned: (1) hypothesis testing using Poisson regression testing the differences in lockout events between the two intervention groups, (2) analysis of possible covariates (e.g., sex, ethnicity, and age of DWI offenders and CFMs), added to the Poisson regression and (3) other exploratory analyses.

**Preliminary Analysis of Baseline Data.** Descriptive data at baseline, with comparisons by treatment group, will be examined to check distributional characteristics and assess any concerns for imbalances that might be considered as covariates in analyses. The potential meaning of non-normality will be examined, i.e., excessive skewness potentially identifying key subgroups. These analyses will be at the level of the individual DWI offenders and CFMs responses and be conducted within 3 months of completion of recruitment. If there is excessive skewness on the IID lockout rates, negative binomial regression will be used.

**Planned Analysis for Hypothesis 1.** The second major analysis will focus on impact of the *B-SMART mobile web app* on primary (IID lockout events) and secondary (DWI offender's alcohol consumption) outcomes, and be completed within 1 month of the end of the posttest data collection in Year 2. The effect of *B-SMART* on IID lockout events in Hypothesis 1 will be tested primarily using PROC GENMOD with a Poisson link via SAS Version 9.4, which includes capabilities to test these Poisson models with missing data, account for the temporal design, and include information by participant. Participants will be treated as a random effect and treatment as a fixed effect, at  $p=0.05$  (2-sided). Analyses of primary outcomes will not be released before completion of the intervention. Since CFM and DWI offender can be clustered within the same family, hierarchical models with participants nested within families will be considered.

The secondary outcome of quantity and frequency of alcohol consumption by DWI offenders will be compared in several ways. Quantity and frequency will be evaluated using Poisson models, as well as a

composite variable based on total alcohol consumption (the product of the two variables), using negative binomial regression models, unless a Poisson model is sufficient.

Since date of IID lockout events will be collected and alcohol consumption is measured at all three assessments, we will examine the time by treatment interaction in the analyses of Hypothesis 1 to assess the question of the durability of the effects of B-SMART over time. For example, we will evaluate time to first lockout using a Kaplan Meier approach and the times to subsequent lockouts.

**Mediation Analysis for Hypothesis 2.** To address the predicted mediation effects of family function on improving the effect of the *B-SMART mobile web app* in Hypothesis 2, we will assess a formal effect on predicting fewer IID lockout events. Mediation will be tested by applying regression techniques from Judd and Kenny and elaborated by MacKinnon, with significance of mediation determined via interval estimation using bootstrapping. Ratio of indirect to total effects will estimate the proportion of the effect mediated. The primary mediational analysis will rely on temporal order of the posttests by examining the effect of *B-SMART* on change in the mediators from baseline to 3-month follow-up and in turn their association with changes in the IID lockout events from baseline to the 9-month follow-up and from 3- to 9-month follow-up.

**Ancillary Analysis of Moderators.** Potential moderators (see 3C.7.3) will be tested at  $p=.05$  (2-tailed) unadjusted for multiple tests. For Hypothesis 1, they will be added as interactions by condition in a manner similar to regression testing for effect modification. Gender is included to probe differences by sex of student and employee. For Hypothesis 2, we will explore if improvements in IID lockout events produced by increases in family function by different participant groups (gender, ethnicity, etc.), using moderated mediational analyses. Moderation effects must be large to be detected, so these are ancillary tests.

**Ancillary Analysis of the *B-SMART Mobile Web App* Exposure.** The same mediational analysis techniques described in 3C.8.4 will be used to explore the relationship of exposure to the *B-SMART mobile web app* and pre-post changes in IID lockout events. Summed scores on exposure will be calculated from the SQL database (e.g., time on app, number of visits to the app, etc.) to assess intervention exposure.

A description of this study will be made available on <http://www.ClinicalTrials.gov>, as required by U.S. Law. This website will not include information that can identify participants. At most, the website will include a summary of the results. This website can be searched at any time. The PI will ensure that the project is registered and results are submitted to ClinicalTrials.gov according to specific timelines as outlined in the Final Rule for Clinical Trials Registration and Results Information Submission (42 CFR Part 11). All informed consent documents will include a specific statement relating to posting of clinical trial information at ClinicalTrials.gov as outlined in the policy.

To ensure compliance, the PI and Project Coordinators will review the Final Rule Webinar Series and Protocol Registration and Results System (PRS User's Guide) and confirm understanding of knowledge and procedures with the Klein Buendel, Inc. (KB) Compliance Officer. KB (applicant organization) has a Quality Control procedure in place for registering all required data into ClinicalTrials.gov. The PI will be the responsible party for ensuring all documents are uploaded based on Final Rule policy. The KB Compliance Officer will independently monitor the timeliness of the uploads and will provide direct communication with the Multiple PIs if a procedure is out of compliance. A formal internal policy is in place to ensure that clinical trials registration and results reporting occur in compliance with policy requirements.

The *B-SMART* mobile web app will be disseminated commercially as described in the Commercialization Plan. The Commercialization Plan addresses five different potential markets for commercialization of *B-SMART*: 1) DWI Offenders with Court-mandated Ignition Interlock Devices, an estimated 300,000 users; 2) Ignition Interlock Device Manufacturing Companies, eight different companies currently in the market; 3) DWI Schools – almost 3700 schools typically working under the auspices of court systems currently exist in the U.S.; 4) Magistrate and DWI Courts – which oversee and supervise the remedial and probation activities of offenders and sentence offenders to Ignition Interlock Device use; and 5) Automobile Insurance Associations, Companies, Agents and Brokers – whose business practices and policies are greatly affected by DWI convictions. These five separate markets hold great potential for the commercialization of *B-SMART*.

**Delayed Onset Studies**

Delayed Onset Study#	Study Title	Anticipated Clinical Trial?	Justification
The form does not have any delayed onset studies			

## STATISTICAL ANALYSIS PLAN

### Sample Size Determination

The sample size for the randomized trial in the Phase II research is designed to provide sufficient information for Phase III commercialization. The sample size assumes the counts of interlocks are Poisson distributed. We have assumed 4 interlocks over 9 months in the control arm or a rate of 0.44 per month for each DWI offender. In the *B-SMART mobile web app* group, we have assumed a reduction of 40% from 0.44, resulting in a rate of 0.27 per month. The null hypothesis is that the ratio of these two rates is 1.0 versus 0.6. Assuming a Type I error of 0.05 (2-sided), 90% power, sample size is only 27 DWI offenders per group. However, if the rate is higher up to 1 per month, the sample size required declines since the percent reductions yield wider absolute differences in the rates. We also are keen to know the reductions achievable with the *B-SMART* group, so we evaluated the sample size with regards to other effect sizes. In a Cochrane meta-analysis reported the impact of IIDs to reduce risk by 64%, but with a confidence interval that ranged from 76% to 37%. In the proposed trial, we have two treatment groups and may see less impact than that in the meta-analysis. Thus, a sample size of 119 DWI offenders per group will allow for 90% power with a comparison of 0.44 to 0.36 or approximately a 20% reduction in interlocks. We will adjust for an expected 15% attrition and this sample size also has sufficient sample size to evaluate the impact in various gender and ethnic subgroups. Thus, we propose to randomize 150 DWI offenders and 150 CFMs to each arm of the trial.

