### 3A.4. Interlock Ignition Device (IID) Research

With the advent of the technology to support the development of IIDs in 1970, these devices have become more sophisticated technologically, allowing digital photography of the driver, WiFi connection to device providers and court systems that allow immediate data transmission of lockout events, and GPS monitoring of driving and breath-testing events. They have also become more widespread in use, with estimates of 300,000 in use among DWI offenders. All 50 U.S. states have some type of IID law, with 25 U.S. states having mandatory IID laws for all DWI offenses. All 50 U.S. states have some type of Ignition Interlock law, with 25 U.S. states having mandatory Ignition Interlock laws for all DWI offenses. Research on the effectiveness of IIDs has shown:

1) IID's reduce the incidence of DWI recidivism while installed in the offender's vehicle, but not once the IID is removed and 2) the frequency of a DWI offender being prevented from starting a vehicle because of a lockout event (the IID sensing the presence of alcohol and disallowing the vehicle to start) predicts DWI recidivism – the more frequent the lockout events, the more likely an offender will have a subsequent DWI arrest. These findings have led researchers to consider ways to extend the effectiveness of IIDs beyond their installation period, including implementing health promotion and treatment programs tied to IID use while in place in offenders' vehicles. Most recently, Voas and colleagues have shown that requiring alcohol treatment of DWI offenders who have frequent IID lockout events resulted in a one-third reduction in DWI recidivism. has recommended increased attention to programs that integrate health promotion interventions while the offender has an IID installed in their vehicle. To date however, no research has examined the impact of family-based treatment on reducing IID lockout events and subsequent DWI recidivism or the provision of family-based treatment via smartphone apps to achieve lockout event reduction and subsequent DWI recidivism. The current investigation will examine this important possibility.

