**3C.6.5. Sample Size Determination.** The sample size for the randomized trial in the Phase II research is designed to provide sufficient information for Phase III commercialization. The sample size assumes the counts of interlocks are Poisson distributed. We have assumed 4 interlocks over 9 months in the control arm or a rate of 0.44 per month for each DWI offender. In the *B-SMART mobile web app* group, we have assumed a reduction of 40% from 0.44, resulting in a rate of 0.27 per month. The null hypothesis is that the ratio of these two rates is 1.0 versus 0.6. Assuming a Type I error of 0.05 (2-sided), 90% power, sample size is only 27 DWI offenders per group. However, if the rate is higher up to 1 per month, the sample size required declines since the percent reductions yield wider absolute differences in the rates. We also are keen to know the reductions achievable with the *B-SMART* group, so we evaluated the sample size with regards to other effect sizes. A Cochrane meta-analysis reported the impact of IIDs to reduce risk by 64%, but with a confidence interval that ranged from 76% to 37%. In the proposed trial, we have two treatment groups and may see less impact than that in the meta-analysis. Thus, a sample size of 119 DWI offenders per group will allow for 90% power with a comparison of 0.44 to 0.36 or approximately a 20% reduction in interlocks. We will adjust for an expected 15% attrition and this sample size also has sufficient sample size to evaluate the impact in various gender and ethnic subgroups. Thus, we propose to randomize 150 DWI offenders and 150 CFMs to each arm of the trial.

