### Outcome Analysis Plan

The trial is intended to evaluate the following hypotheses:

**H1:** First-time DWI offenders in the intervention group (*B-SMART mobile web app*) will have significantly fewer IID lockout events than participants in the control group (UC information condition).

**H2:** Lower rates of IID lockout events will be mediated by improvements in Family Functioning, Family Communication, and Shared Positive Family Events in the intervention (*B-SMART mobile web app*) condition compared to the UC information condition.

We will also analyze the moderation of the effect of *B-SMART* by demographics and mediation of IID lockout events by *B-SMART* use in the intervention group.

Three levels of analysis are planned: (1) hypothesis testing using Poisson regression testing the differences in lockout events between the two intervention groups, (2) analysis of possible covariates (e.g., sex, ethnicity, and age of DWI offenders and CFMs), added to the Poisson regression and (3) other exploratory analyses.

**Preliminary Analysis of Baseline Data.** Descriptive data at baseline, with comparisons by treatment group, will be examined to check distributional characteristics and assess any concerns for imbalances that might be considered as covariates in analyses. The potential meaning of non-normality will be examined, i.e., excessive skewness potentially identifying key subgroups. These analyses will be at the level of the individual DWI offenders and CFMs responses and be conducted within 3 months of completion of recruitment. If there is excessive skewness on the IID lockout rates, negative binomial regression will be used.

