**Planned Analysis for Hypothesis 1.** The second major analysis will focus on impact of the *B-SMART mobile web app* on primary (IID lockout events) and secondary (DWI offender's alcohol consumption) outcomes and be completed within 1 month of the end of the posttest data collection in Year 2. The effect of *B-SMART* on IID lockout events in Hypothesis 1 will be tested primarily using PROC GENMOD with a Poisson link via SAS Version 9.4, which includes capabilities to test these Poisson models with missing data, account for the temporal design, and include information by participant. Participants will be treated as a random effect and treatment as a fixed effect, at  $p=0.05$  (2-sided). Analyses of primary outcomes will not be released before completion of the intervention. Since CFM and DWI offender can be clustered within the same family, hierarchical models with participants nested within families will be considered.

The secondary outcome of quantity and frequency of alcohol consumption by DWI offenders will be compared in several ways. Quantity and frequency will be evaluated using Poisson models, as well as a composite variable based on total alcohol consumption (the product of the two variables), using negative binomial regression models, unless a Poisson model is sufficient.

Since date of IID lockout events will be collected and alcohol consumption is measured at all three assessments, we will examine the time by treatment interaction in the analyses of Hypothesis 1 to assess the

question of the durability of the effects of B-SMART over time. For example, we will evaluate time to first lockout using a Kaplan Meier approach and the times to subsequent lockouts.

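### The 90% power for a 20% reduction in lockouts holds only if counts vary no more than Poisson; the H1 model is described in three ways, and the trigger for negative binomial is undefined

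*Combined protocol and SAP*

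**What the plan says.** The SAP's Sample Size Determination (same calculation in protocol 3C.6.5 and item 4.4) states: "The sample size assumes the counts of interlocks are Poisson distributed". It takes 4 events per control offender over 9 months, two-sided alpha 0.05 and 90% power. A 40% reduction needs 27 per group. For the smaller effect: "Thus, a sample size of 119 DWI offenders per group will allow for 90% power with a comparison of 0.44 to 0.36", described as roughly a 20% reduction. It then adds: "We will adjust for an expected 15% attrition", and arrives at 150 offenders per arm. It also says that "if the rate is higher up to 1 per month, the sample size required declines".

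The model for H1 is described in three ways:

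- The list of analysis levels in the SAP's Outcome Analysis Plan gives Poisson regression.
- Planned Analysis for Hypothesis 1 gives a Poisson model in which "Participants will be treated as a random effect and treatment as a fixed effect".
- Preliminary Analysis of Baseline Data says: "If there is excessive skewness on the IID lockout rates, negative binomial regression will be used".

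For the composite alcohol outcome the order is reversed. It is analysed "using negative binomial regression models, unless a Poisson model is sufficient".

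**The concern.** A Poisson sample size assumes that every offender in an arm has the same underlying lockout rate. A participant random effect and a negative binomial model both exist to let rates differ between offenders. Protocol 3A.4 reports that "the more frequent the lockout events, the more likely an offender will have a subsequent DWI arrest", which presupposes that offenders differ, though it does not say by how much. The power figure therefore omits a source of variance that two of the three model descriptions allow for.

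Two things are at stake. First, the 20% scenario led to 119 and so to 150 per arm. A null result would be read as 90%-powered evidence against a 20% reduction, and whether that is fair depends on a dispersion that the plan never states. Second, the choice of primary model is left open. Excessive skewness has no statistic or threshold attached. It is also the wrong quantity: a pure Poisson count with mean 4 has skewness 1/√4 = 0.5 with no overdispersion at all. What matters is variance relative to the mean. The rule also sits in a baseline review due within 3 months of the end of recruitment. Recruitment runs to month 11 (3C.6.1), so that review falls by month 14. Lockout counts are acquired only at each offender's 9-month point, up to month 20.

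**Working it through.** **Inputs from the documents.** Control mean 4 events over 9 months; reductions of 40% (mean 2.4) and 20% (mean 3.2); two-sided alpha 0.05; 90% power; 150 randomized per arm. The number with a full count is not settled. Section 3C.6.1 plans to collect lockouts for all offenders, which gives 150. The retention plan (item 2.5) expects 255 completers, and 255/2 = 127.5, taken as 127.

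**Input not in the documents.** Overdispersion k, with variance = mean + k × mean². I show k = 0, 0.1, 0.25, 0.5 and 1. At a mean of 4 these are variance-to-mean ratios of 1, 1.4, 2, 3 and 5.

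**Formula.** n per arm = (1.960 + 1.2816)² × (1/m0 + 1/m1 + 2k) / [ln(m1/m0)]², where (1.960 + 1.2816)² = 10.507.

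**Reproducing the plan (k = 0).**
- 40%: 10.507 × (0.25 + 0.4167) / 0.2609 = 26.8, so 27, as stated.
- 20%: 10.507 × (0.25 + 0.3125) / 0.04979 = 118.7, so 119, as stated.
- This reads 0.36 as 3.2/9 = 0.356. The printed rates taken literally (0.44 × 9 = 3.96 against 0.36 × 9 = 3.24, an 18% reduction) give about 146.

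Both stated figures therefore contain Poisson variance only.

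**Power for a 20% reduction at 4 control events.** Power = Φ(|ln 0.8| / √[(0.5625 + 2k)/n] − 1.960).

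| k | 0 | 0.1 | 0.25 | 0.5 | 1 |
|---|---|---|---|---|---|
| 150 per arm | 95% | 88% | 76% | 59% | 40% |
| 127 per arm | 92% | 82% | 68% | 52% | 35% |

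A simulation with 150 per arm, gamma-distributed rates and a robust-variance test agreed to within about 1 point (96%, 88%, 76%, 59%, 40%).

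**Largest k that keeps 90% power.** Solving for k: k = [n × (ln ratio)² / 10.507 − (1/m0 + 1/m1)] / 2.

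| Scenario | 150 per arm | 127 per arm |
|---|---|---|
| 20% reduction, 4 control events | 0.07 | 0.02 |
| 20% reduction, 9 control events | 0.23 | 0.18 |
| 40% reduction, 4 control events | 1.5 | 1.2 |

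**Reduction detectable with 90% power at 4 control events.**

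| k | 0 | 0.1 | 0.25 | 0.5 | 1 |
|---|---|---|---|---|---|
| 150 per arm | 18% | 21% | 24% | 28% | 35% |
| 127 per arm | 19% | 22% | 26% | 31% | 37% |

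**Effect of a higher rate.** For a 20% reduction, going from 4 to 9 control events takes n per arm from 119 to 53 at k = 0, but only from 330 to 264 at k = 0.5.

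**Type I error if H1 were fitted as plain Poisson.** At 4 events, 2 × [1 − Φ(1.96/√(1 + 4k))] gives about 17% at k = 0.25 and 26% at k = 0.5.

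**The case against.** The strongest reply is that the plan states its Poisson assumption openly, 119 is correct under it, and no document gives a dispersion. That stands. A reader might infer that the trial is shown to be underpowered or that 119 is miscalculated. The documents support neither. What they show is a 90% that depends on an unstated quantity and tolerates very little of it.

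Three further replies have weight. The hypothesis is framed as a ratio of 1.0 against 0.6, and that scenario is robust. But 27 per group did not set the trial size; the 20% scenario did. Second, the tight limits on k apply at 4 control events, and at the plan's upper rate of 1 per month they are looser. Four events is still the base case. Third, lockouts come from program records, so survey loss need not reduce the count data. Against that, the sample size text allows for 15% attrition, and section 3.2.A stops data collection on withdrawal, so both 150 and 127 are shown.

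It is also tempting to say that type I error will be inflated. That follows only if H1 is fitted as plain Poisson with no dispersion correction. The analysis-levels list can be read that way; the Hypothesis 1 text, with its random effect, cannot.

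The study structure section has a subcommittee writing a detailed analysis plan, which could define the trigger. The SAP supplied does not.

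**Conclusion.** The point holds in a conditional form. The 90% power for a 20% reduction is valid only when the 9-month count has variance close to its mean. At 4 control events the tolerance is k of about 0.07 with 150 per arm analysed (control variance 1.30 times the mean) and 0.02 with 127 (1.08 times). At 9 events it is about 0.23 and 0.18. The direction of the effect is certain, since any overdispersion lowers power. Its size is not, because k is assumed throughout. The 40% scenario keeps 90% power to k of about 1.2 or more. Separately, the primary model is not fixed: there are three descriptions, and the switch between them rests on an undefined and unsuitable criterion. This should be corrected before outcome data are seen, but it does not invalidate the design.

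**What to change.** 1. **Primary model.** Make negative binomial regression with log link, on the 9-month lockout count with one record per offender, the single primary H1 model. It replaces the Poisson default, the participant random effect for this count and the skewness trigger. Use Poisson regression with robust variance as the sensitivity analysis.
2. **Power statement.** In all three copies of the sample size text (protocol 3C.6.5, item 4.4 and the SAP), say that the 90% assumes no overdispersion. Add the detectable reductions at 4 control events for k = 0, 0.1, 0.25, 0.5 and 1: 18%, 21%, 24%, 28% and 35% with 150 analysed per arm; 19%, 22%, 26%, 31% and 37% with 127. Label k as an assumption, or give its source.
3. **Higher-rate sentence.** Qualify it: for a 20% reduction, moving to 1 event per month cuts n from 119 to 53 per arm at k = 0, but only from 330 to 264 at k = 0.5.

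The cost is wording in the protocol and SAP, and a less favourable power statement. No added participants or data are needed.
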